10.2 Exclusion Criteria

Subjects must NOT meet any of the following exclusion criteria:

1. Use of systemic antibiotics effective in cUTI within 72 hours prior to randomization EXCEPT under the following circumstances:
 - a. Subjects with suspected acute cUTI who have received a single dose of effective non-study antibiotics for the acute cUTI
 - b. Signs and symptoms of cUTI developed while on the antibiotic for another indication
2. History of an ertapenem-resistant urinary tract infection within 1 year of consent
3. Likely to require > 10 days of antibiotic treatment to cure the acute cUTI or likely to receive ongoing antibacterial drug prophylaxis prior to the FU visit (eg. Subjects with chronic vesiculo-ureteral reflux).
4. Unlikely to survive at least through the duration of the study
5. Hypotension, systolic blood pressure ≤ 90 mmHg
6. Complicated pyelonephritis with complete obstruction or known or suspected renal or perinephric abscess, emphysematous pyelonephritis, **OR**
Any condition likely to require surgery to achieve cure (this does NOT include procedure to place catheters or obtain diagnosis)
7. Known or suspected urinary fungal infection
8. Uncomplicated lower urinary tract infections
9. Suspected or confirmed active prostatitis, or currently under treatment for prostatitis
10. High risk for cUTI due to *Pseudomonas sp.* (eg, history of prior cUTIs due to *Pseudomonas*, ≥ 20 mg QD prednisone or equivalent steroid, and other risk factors as perceived by the Investigator)
11. History of renal transplantation
12. Presence of an ileal loop
13. Any history of trauma to the pelvis or urinary tract occurring within 30 days prior to consent
14. Indwelling urinary catheters present at screening which are not expected to be removed or replaced within 72 hours of randomization (eg, nephrostomy tubes, stents, urethral and suprapubic catheters).
15. Known concomitant HIV infection with CD4 counts below 200 cells/ μ L within six months prior to consent, or an AIDS defining diagnosis within six months prior to consent
16. Neutropenia (ANC < 1,000 PMNs/ μ L)
17. Participation in a study with an experimental drug or device within 30 days prior to consent

18. Known or suspected hypersensitivity to tetracyclines, carbapenems, or β -lactams
19. History of seizures

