Baseline is defined as the value closest to but prior to the start of study drug administration. Analyses will utilize assessments occurring during safety analysis windows (see [Table 2](#)). Thus, if a subject has a visit outside the window, for example, a TOC visit on Day 11, the laboratory assessment will not be summarized with the TOC visit but will be considered an unscheduled assessment. If more than 1 measurement is taken during the visit window, the value taken on the scheduled visit will be utilized or if no scheduled visit was done, the first (earliest) measurement will be used. If more than 1 measurement is taken on the same day, the last measurement on the day will be used. For worst overall post-baseline analyses, all laboratory assessments including those obtained from unscheduled visits will be included.

Several analyses of the laboratory data will be presented. Descriptive statistics (based on SI units) for chemistry, hematology and coagulation values and the change from baseline will be summarized by treatment group at Day 5, EOI, EOT, TOC and FU visits, and for the overall worst value post-baseline (which includes unscheduled visits). Change from baseline will be calculated for each patient at the specified time point as the value at the specified time point minus the baseline value.

Toxicity grade will be determined based on the modified Division of Microbiology and Infectious Diseases (DMID) criteria in [Table 7](#). The DMID Adult Toxicity Table (November 21, 2007) was modified to exclude the clinical component of the toxicity grading. In addition, Grade 0 was added to the table so that shifts from normal could be analyzed. For toxicity grades based on a multiple of the ULN, the normal range from the central laboratory will be applied. For toxicity grades based on fixed values, the grades will be assigned regardless of the normal actual range values from the central laboratory. For example, a hemoglobin value of 10.0 gm/dL will be assigned a grade of 1 toxicity, even if the lower limit of normal from the laboratory was 9.8 gm/dL. Shift tables will be presented to show the number of subjects with a laboratory value with a grade of 0, 1, 2, 3 or 4 at baseline versus the worst post-baseline value.

Table 7 Modified Division of Microbiology and Infectious Diseases Adult Toxicity Criteria (November, 2007)

Hematology					
	Grade 0	Grade 1	Grade 2	Grade 3	Grade 4
Hemoglobin (gm/dL)	>10.5	9.5-10.5	8.0-9.4	6.5-7.9	<6.5

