Absolute Neutrophil Count (count/mm ³)	>1,500	1,000-1,500	750-999	500-749	<500
Platelets (counts/mm ³)	≥100,000	75,000-99,999	50,000-74,999	20,000-49,999	<20,000
WBC (count/mm ³)	1,000-10,999	11,000-12,999	13,000-14,999	15,000-30,000	>30,000

% Polymorphonuclear Leucocytes	≤80%	>80%-90%	>90-95%	>95%	--
--------------------------------	------	----------	---------	------	----

Key: WBC = White Blood Cell Count.

Chemistry					
	Grade 0	Grade 1	Grade 2	Grade 3	Grade 4
Hyponatremia (mEq/L)	>135	130-135	123-129	116-122	<116
Hypernatremia (mEq/L)	<146	146-150	151-157	158-165	>165
Hypokalemia (mEq/L)	>3.4	3.0-3.4	2.5-2.9	2.0-2.4	<2.0
Hyperkalemia (mEq/L)	<5.6	5.6-6.0	6.1-6.5	6.6-7.0	>7.0
Hypoglycemia (mg/dL)	≥65	55-64	40-54	30-39	<30
Hyperglycemia (mg/dL) (nonfasting and regardless of prior history of diabetes)*	<116	116-160	161-250	251-500	>500
Hypocalcemia (mg/dL) (corrected for albumin)	>8.4	7.8-8.4	7.0-7.7	6.1-6.9	<6.1
Hypercalcemia (mg/dL)	≤10.5	10.6-11.5	11.6-12.5	12.6-13.5	>13.5
Hypomagnesemia (mEq/L)	>1.4	1.2-1.4	0.9-1.1	0.6-0.8	<0.6
Hypophosphatemia (mg/dL)	≥2.5	2.0-2.4	1.5-1.9	1.0-1.4	<1.0
Hyperbilirubinemia (total bilirubin)	<1.1×ULN	1.1-1.5×ULN	1.6-2.5×ULN	2.6-5.0×ULN	>5.0×ULN
BUN	<1.25×ULN	1.25-2.5×ULN	2.6-5.0×ULN	5.1-10.0×ULN	>10.0×ULN
Hyperuricemia (uric acid) (mg/dL)	<7.5	7.5-10.0	10.1-12.0	12.1-15.0	>15.0
Creatinine	<1.1×ULN	1.1-1.5×ULN	1.6-3.0×ULN	3.1-6.0×ULN	>6.0×ULN

Key: BUN = Blood Urea Nitrogen; ULN = Upper Limit of Normal.

* The DMID toxicity table reports hyperglycemia detected in nonfasting specimens obtained from patients with no prior diabetes.

Enzymes					
	Grade 0	Grade 1	Grade 2	Grade 3	Grade 4
AST (SGOT)	<1.25×ULN	1.25-2.5×ULN	2.6-5×ULN	5.1-10×ULN	>10×ULN
ALT (SGPT)	<1.25×ULN	1.25-2.5×ULN	2.6-5×ULN	5.1-10×ULN	>10×ULN
GGT	<1.25×ULN	1.25-2.5×ULN	2.6-5×ULN	5.1-10×ULN	>10×ULN
Alkaline Phosphatase	<1.25×ULN	1.25-2.5×ULN	2.6-5×ULN	5.1-10×ULN	>10×ULN
Amylase	<1.1×ULN	1.1-1.5×ULN	1.6-2.0×ULN	2.1-5.0×ULN	>5.1×ULN
Lipase	<1.1×ULN	1.1-1.5×ULN	1.6-2.0×ULN	2.1-5.0×ULN	>5.1×ULN

Key: ALT (SGPT) = Alanine Aminotransferase (Serum Glutamic Pyruvic Transaminase); AST (SGOT) = Aspartate Aminotransferase (Serum Glutamic Oxaloacetic Transaminase); GGT = Gamma-Glutamyl Transferase; ULN = Upper Limit of Normal.

COAGULATION					
	Grade 0	Grade 1	Grade 2	Grade 3	Grade 4
Fibrinogen (mg/dL)	>200 - <400	100-200 (low) or 400-600 (high)	50 - <100 (low) or >600 (high)	<50 (low)	Fibrinogen associated with gross bleeding or with disseminated coagulation

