Activated Partial Thromboplastin (APPT)	<1.01×ULN	1.01-1.66×ULN	1.67-2.33×ULN	2.34-3×ULN	>3×ULN
Prothrombin Time (PT)/International Normalized Ratio (INR)	<1.01×ULN	1.01-1.25×ULN	1.26-1.5×ULN	1.51-3.0×ULN	>3×ULN

Key: ULN = Upper Limit of Normal.

Number and percentage of subjects with at least a 2-grade increase from baseline or a post-baseline grade 4 abnormality (based on DMID criteria) will be summarized by treatment arm. Percentages for each lab test will be based on the number of subjects with a post-baseline evaluation of that laboratory test. A table will be provided which gives all laboratory results for a given laboratory test for subjects who have at least one 2-grade increase from baseline or a post-baseline grade 4 abnormality.

The number and percentage (based on the number of subjects with a normal level at baseline) of subjects in each treatment group with an elevated transaminase level ($>3 \times \text{ULN}$, $>5 \times \text{ULN}$, and $>10 \times \text{ULN}$), an elevated bilirubin level ($>1.5 \times \text{ULN}$ and $>2 \times \text{ULN}$) will be presented by study visit. A table of subjects who meet the laboratory criteria for Hy's law will also be provided. The laboratory criteria for Hy's law is defined as ALT or AST $>3 \times \text{ULN}$, ALP $\leq 2.0 \times \text{ULN}$, and total bilirubin $>2 \times \text{ULN}$.

Detailed patient listings of all laboratory data collected during the study will be provided. Laboratory values outside normal limits will be identified in the patient data listings with flags for low (L) and high (H) as will laboratory values that meet the clinically notable (CN) thresholds.

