5.8.3. Vital Signs and Physical Examination

Blood pressure (systolic and diastolic), respiration rate, and heart rate will be summarized using descriptive statistics by treatment group at each time point at which they were measured. Descriptive statistics of the change from baseline to each post-baseline time point will also be provided. Change from baseline will be calculated for each subject at the specified time point as the value at the specified time point minus the baseline value. Visit windows will be determined in the same manner as described for the laboratory data. Clinically significant physical examination findings will be reported, analyzed and presented as AEs.

A summary of abnormal values, identified by the threshold levels provided in [Table 8](#) will be analyzed using the methodology described for CN laboratory values with the exception that only subjects with both baseline and post-baseline values will be evaluable for the analysis of a diastolic blood pressure increase >20 mmHg.

Table 8 Clinically Notable Abnormal Vital Sign Threshold Values

ABNORMAL VALUES		
Vital Sign	Threshold	Reference
Diastolic blood pressure	> 20 mmHg increase from baseline	CTCAE Grade 2
Systolic blood pressure	\geq 140 mmHg	CTCAE Grade 2
Heart rate	< 60 beats/min	Noble et al 1990
Heart rate	> 120 beats/min	-

Key: CTCAE = Common Terminology Criteria for Adverse Events, Version 4.0

Detailed patient listings of all vital signs results will be provided.

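### SAP Table 7 grades low and high fibrinogen on one scale, so the graded tables miss or understate falls from a baseline of 400 mg/dL or more; low WBC and low blood pressure also lack a category

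*SAP*

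**What the plan says.** **Fibrinogen.** SAP 5.8.2, Table 7, has one row (mg/dL). Grade 0 is above 200 and below 400. Grade 1 is "100-200 (low) or 400-600 (high". Grade 2 is "50 - <100 (low) or >600 (high". Grade 3 is below 50. Grade 4 is "Fibrinogen associated with gross bleeding or with disseminated coagulation". The text before the table says that the source toxicity table "was modified to exclude the clinical component of the toxicity grading". Sodium, potassium, glucose and calcium each have separate low and high rows.

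**WBC.** Grade 0 is 1,000 to 10,999 per mm³ and Grades 1 to 4 start at 11,000 and rise. Nothing is defined below 1,000. The absolute neutrophil count (ANC) has its own row, graded downward.

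**ULN multiples.** Total bilirubin and creatinine step from 1.5 to 1.6, ALT and AST from 2.5 to 2.6. Amylase and lipase have Grade 3 ending at 5.0 and Grade 4 starting above 5.1.

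**Use of the grades.** The SAP plans shift tables of baseline grade against worst post-baseline grade, and a count by arm of subjects with "at least a 2-grade increase from baseline or a post-baseline grade 4 abnormality". Protocol 15.2.2 also names the shift tables and the 2-grade count as planned safety outputs.

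**Blood pressure.** SAP 5.8.3, Table 8, marks a diastolic rise of more than 20 mmHg and a systolic value of 140 mmHg or more. Heart rate has a low and a high limit; blood pressure has no low one. Protocol 10.2 excludes "Hypotension, systolic blood pressure ≤ 90 mmHg".

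**The concern.** A grade that means either too low or too high cannot show a crossing from one side to the other. A subject who starts high and ends low may keep the same grade or drop a grade, and the table then reads as no change or recovery. The same happens when a scale runs in only one direction, as for WBC, or when a notable-value table has a limit on only one side, as for blood pressure.

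The shift tables and the 2-grade count are the planned outputs that count affected subjects by arm for these laboratory tests. Mean changes do not count subjects, and listings do not compare arms. If the graded tables misclassify falls, a reader of the study report who relies on them will see too few cases of low fibrinogen, low WBC or low blood pressure.

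**Working it through.** **Check of the reading.** The SAP gives one worked example: hemoglobin 10.0 gm/dL is Grade 1. The printed cut points (Grade 1: 9.5 to 10.5) reproduce it.

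**Fibrinogen.** Change in grade = post-baseline grade minus baseline grade; a subject is flagged if the change is 2 or more, or if the post-baseline grade is 4. The post-baseline value is taken as the worst one. The split column uses only the SAP's own low-side cut points: Grade 0 above 200, Grade 1 100 to 200, Grade 2 50 to <100, Grade 3 below 50.

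| Baseline to post (mg/dL) | SAP grades | Change | Flagged | Split low row | Flagged |
|---|---|---|---|---|---|
| 300 to 75 | 0 to 2 | +2 | yes | 0 to 2 | yes |
| 300 to 40 | 0 to 3 | +3 | yes | 0 to 3 | yes |
| 450 to 60 | 1 to 2 | +1 | no | 0 to 2 | yes |
| 500 to 40 | 1 to 3 | +2 | yes | 0 to 3 | yes |
| 650 to 60 | 2 to 2 | 0 | no | 0 to 2 | yes |
| 650 to 150 | 2 to 1 | -1 | no | 0 to 1 | no |
| 700 to 40 | 2 to 3 | +1 | no | 0 to 3 | yes |

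The general rule follows from the cut points:
- Baseline >200 to <400 (Grade 0): any value below 100 is at least +2 and is flagged.
- Baseline 400 to 600 (Grade 1): a flag needs Grade 3, so only values below 50 qualify; 50 to <100 is missed.
- Baseline above 600 (Grade 2): a flag needs Grade 4, which has no laboratory value. No fall can be flagged.

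The fall from 650 to 150 stays below the 2-grade rule even on a split row. What changes is the shift table: improvement becomes Grade 0 to 1.

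**WBC.** 14,000 to 1,500 is Grade 2 to 0. 8,000 to 1,000 is Grade 0 to 0. 8,000 to 900 has no post-baseline grade. No fall can be flagged on this row.

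**ANC as a partial cover.** Neutrophils are part of the WBC, so WBC 900 implies ANC of 900 or less, which is ANC Grade 2 (750 to 999) or worse. From a baseline ANC above 1,500 (Grade 0) that is at least +2 and is flagged. Protocol 10.2 excludes ANC below 1,000, so an eligible subject starts at ANC Grade 0 or 1. From Grade 1, a fall to 900 is +1 and is not flagged. Low WBC with neutrophils above 1,500 is not graded anywhere.

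**Blood pressure.** 120/75 to 80/45 meets neither blood pressure limit in Table 8. 145/90 to 85/50 moves from above the systolic limit to not notable.

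**Gaps.** As printed, bilirubin or creatinine at 1.55×ULN and ALT at 2.55×ULN have no grade. Rounding to one decimal would close these, but the SAP states no rounding rule. For amylase and lipase rounding is not enough: 5.1×ULN is above 5.0 and not above 5.1.

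**The case against.** The strongest reply is that the safety plan does see falls. Table 7 grades hemoglobin, ANC and platelets downward, as well as low sodium, potassium, glucose, calcium, magnesium and phosphorus, and Table 8 has a low heart rate limit. Hematology, coagulation and blood pressure all have descriptive summaries of change from baseline. Laboratory box plots show the minimum by arm and visit, and listings carry low flags. Protocol 13.2 makes clinically relevant deterioration in laboratory or other clinical findings an adverse event, and adverse events are tabulated by arm. All of this stands. A reader might infer that the plan is blind to falls, or that a difference between arms would be hidden or reversed in the safety results as a whole; these outputs show that the documents do not support that.

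It is also fair that fibrinogen is affected only from a baseline of 400 mg/dL, that ANC covers much of severe leukopenia, and that most ULN gaps may be a matter of rounding. Table 7 is a modified external scale, and the documents do not show which features were inherited. The documents set no low-side WBC grades, and the 90 mmHg figure is an entry criterion, not a stated safety limit.

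None of this repairs the tables. The combined fibrinogen row gives a wrong grade change for some subjects, and its Grade 4 contradicts the SAP's statement that the clinical component was removed.

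**Conclusion.** The point holds for the graded and notable-value tables, and only for them. For fibrinogen the error is certain from the cut points: with a baseline of 400 to 600 mg/dL, falls to 50 to <100 are not flagged; above 600, no fall is. From >200 to <400, falls below 100 are flagged correctly. WBC falls are never flagged on the WBC row, with partial cover from ANC. Low blood pressure is never marked in Table 8.

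How many subjects this touches cannot be derived. It depends on the share with baseline fibrinogen of 400 or more, which the documents do not give and which could lie anywhere from 0% to 100%, and on how often such falls occur. A reader might assume that acute infection puts most subjects in that range; the documents give no baseline distribution to support a figure. The change is worth making before lock because the defect is clear and the repair is small.

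**What to change.** Amend the SAP before database lock:

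1. In Table 7, replace the fibrinogen row with two. Low: Grade 0 above 200, Grade 1 100 to 200, Grade 2 50 to <100, Grade 3 below 50. High: Grade 0 below 400, Grade 1 400 to 600, Grade 2 above 600. These are the existing cut points. Delete the clinical Grade 4.
2. Give every WBC value a grade by adding a low-side row with cut points set by the sponsor, or state that ANC is the graded measure of low counts and how WBC below 1,000 is tabulated.
3. Make the ULN-multiple boundaries contiguous, including amylase and lipase between Grades 3 and 4, or state a rounding rule that leaves no gap.
4. Add a low systolic category to Table 8 and reconcile it with the hypotension figure in Protocol 10.2, or justify its absence.

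The cost is minor table edits and programming. No new data are needed, and the efficacy analyses are untouched.

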5.8.3. Vital Signs and Physical Examination

Blood pressure (systolic and diastolic), respiration rate, and heart rate will be summarized using descriptive statistics by treatment group at each time point at which they were measured. Descriptive statistics of the change from baseline to each post-baseline time point will also be provided. Change from baseline will be calculated for each subject at the specified time point as the value at the specified time point minus the baseline value. Visit windows will be determined in the same manner as described for the laboratory data. Clinically significant physical examination findings will be reported, analyzed and presented as AEs.

A summary of abnormal values, identified by the threshold levels provided in [Table 8](#) will be analyzed using the methodology described for CN laboratory values with the exception that only subjects with both baseline and post-baseline values will be evaluable for the analysis of a diastolic blood pressure increase >20 mmHg.

Table 8 Clinically Notable Abnormal Vital Sign Threshold Values

ABNORMAL VALUES		
Vital Sign	Threshold	Reference
Diastolic blood pressure	> 20 mmHg increase from baseline	CTCAE Grade 2
Systolic blood pressure	\geq 140 mmHg	CTCAE Grade 2
Heart rate	< 60 beats/min	Noble et al 1990
Heart rate	> 120 beats/min	-

Key: CTCAE = Common Terminology Criteria for Adverse Events, Version 4.0

Detailed patient listings of all vital signs results will be provided.

6. CHANGES TO PLANNED ANALYSES

This is Version 1.0 of the SAP.

